**PASS information**

Title	A multi-national, multi-centre, prospective, single-arm, observational, non-interventional post-authorisation safety study to investigate long-term safety of Sogroya ® (somapacitan) in adults with growth hormone deficiency (AGHD) under routine clinical practice
Protocol author	██████████ Trial Manager Biopharm ClinOps 5 Novo Nordisk A/S [name]
Protocol version identifier	Version 3.0
Date of last version of protocol	15 February 2022
EU PAS Register number	Study not yet registered
Active substance	ATC code: H01AC07
Medicinal product	Sogroya ®
Product reference	EU/1/20/1501
Procedure number	EMA/H/C/005030/MEA/001
Marketing authorisation holder(s)	Novo Nordisk A/S [name]
Joint Post Authorisation Safety Study (PASS)	No
Research question and objective	
Primary objective
 
To investigate long-term safety of Sogroya® (somapacitan) therapy in patients with Adult Growth Hormone Deficiency (AGHD) in the setting of routine clinical practice with special focus on neoplasms and diabetes mellitus type 2.
 
Secondary objectives
 
To investigate safety and clinical parameters in patients treated with Sogroya® (somapacitan) under routine clinical practice.
 
To investigate safety and clinical parameters of Sogroya® (somapacitan) treatment under routine clinical practice in patients with AGHD for the subgroups childhood-onset GHD and females on oral oestrogen therapy, respectively.

Protocol  
 Study ID: NN8640-4515  
 UTN: U1111-1264-8642  
 EU PAS No: Pending

~~CONFIDENTIAL~~

Date: 15 February 2022  
 Version: 3.0  
 Status: Final  
 Page: 3 of 53 **Novo Nordisk**

	
To investigate the number of patients achieving the age-adjusted IGF-I SDS levels up to the upper limit of the normal reference range (0 and +2).
 
To evaluate the impact of Sogroya® (somapacitan) on patient functioning and wellbeing through a patient reported outcome measure (TRIM-AGHD)
 
Exploratory objective                  Change in number of different anti-diabetic medications for patients with diabetes mellitus type 2 at baseline.
 
To evaluate the impact of Sogroya® (somapacitan) on patient sick days and physician visits, work and study productivity and ability to do regular daily activities through a patient reported outcome measure (AGHD WSI)

Country(-ies) of study	
Countries have not been finalized; the study will be conducted internationally including in all European countries where the product is launched and where treating physicians and patients can be recruited.

**CONFIDENTIAL**

Date: 15 February 2022  
 Version: 3.0  
 Status: Final  
 Page: 5 of 53  

## 2 List of abbreviations

ADR	Adverse drug reaction
AE	Adverse Event
AGHD	Adult Growth Hormone Deficiency
ALT	Alanine transaminase
AR	Adverse Reaction
AST	Aspartate aminotransferase
ATC	Anatomical Therapeutic Chemical (Classification System)
BMI	Body Mass Index
CRA	Clinical Research Associate
CRF	Case Report Form
CV	Curriculum Vitae
DXA	Dual energy x-ray absorptiometry
ECG	Electrocardiogram
eCRF	Electronic Case Report Form
EDC	Electronic Data Capture
ENCePP	European Network of Centres for Pharmacoepidemiology and Pharmacovigilance
EU PAS	The EU electronic register of post-authorisation studies maintained by the European Medicines Agency
FPFV	First Patient First Visit
GGT	Gamma-Glytanyltransferase
GH	Growth Hormone
GHD	Growth Hormone Deficiency
GPP	Good Pharmacoepidemiology Practice
GVP	Good Pharmacovigilance Practice
HDL	High Density Lipoprotein
IEC	Independent Ethics Committee
IGF-I	Insulin-like growth factor I
IGFBP-3	Insulin-like growth factor binding protein -3
IOS	International Outcome Study
IRB	Institutional Review Board
ISPE	International Society for Pharmacoepidemiology
LDL	Low Density Lipoprotein

Protocol  
 Study ID: NN8640-4515  
 UTN: U1111-1264-8642  
 EU PAS No: Pending

~~CONFIDENTIAL~~

Date:  
 Version:  
 Status:  
 Page:

15 February 2022  
 3.0  
 Final  
 8 of 53

**Novo Nordisk**

LPLV	Last Patient Last Visit
MAH	Marketing Authorisation Holder
MedDRA	Medical Dictionary for Regulatory Activities
NIS	Non-interventional Study
PAS	Post Authorisation studies
PASS	Post Authorisation Safety Study
PRO	Patient reported outcome
SAE	Serious Adverse Event
SAR	Serious Adverse Reaction
SAS	Safety Analysis Set
SDS	Standard Deviation Score
s.c	Subcutaneous
SOC	System Organ Class
TMF	Trial Master File
TRIM-AGHD	Treatment Related Impact Measure - Adult Growth Hormone Deficiency
UTN	Universal Trial Number
VV	Veeva Vault
VAT	Visceral adipose Tissue
WHO	World Health Organisation
WMA	World Medical Association
AGHD-WSI	Adult Growth Hormone Deficiency Work Study Impact

Protocol  
 Study ID: NN8640-4515  
 UTN: U1111-1264-8642  
 EU PAS No: Pending

**CONFIDENTIAL**

Date: 15 February 2022  
 Version: 3.0  
 Status: Final  
 Page: 9 of 53  
**Novo Nordisk**

### 3 Responsible parties

In this document physician refers to the individual overall responsible for the conduct of the non-interventional study at a study site.

The physician is accountable for the conduct of the study. If any tasks are delegated, the physician should maintain a list of appropriately qualified persons to whom he/she has delegated specified significant study-related duties. During any period of unavailability, the physician should delegate responsibility for study activities of patients to a specific qualified physician who should be readily available to patients during that time. If the physician is no longer able to fulfil the role of physician (e.g. if he/she retires), a new physician must be appointed in consultation with Novo Nordisk. The physician and site personnel must have sufficient English skills according to their assigned task(s). The physician must follow the instructions from Novo Nordisk when processing data. The physician must take all necessary technical and organisational safety measures to prevent accidental or wrongful destruction, loss or deterioration of data. The physician must prevent any unauthorised access to data or any other processing of data against applicable law. Upon request from Novo Nordisk, the physician must provide Novo Nordisk with the necessary information to enable Novo Nordisk to ensure that technical and organisational safety measures have been taken.

Please refer to the Stand-alone documents ([Annex 1](#)) for additional information about responsible parties. A list of all collaborating institutions and physicians will be made available to authorities upon request.

## 4 Abstract

### 4.1 Title

A multi-national, multi-centre, prospective, single-arm, observational, non-interventional post-authorisation safety study (PASS) to investigate long-term safety of Sogroya® (somapacitan) in adults with growth hormone deficiency (AGHD) under routine clinical practice (version 3.0, dated 15-Feb-2022)

### 4.2 Milestones

Milestone	Planned date
Start of data collection – First patient first visit (FPFV)	15 Dec 2022
Interim report 1	Data cut 3 years following FPFV 15 Dec 2025
Last patient first visit – end of study recruitment	15 Dec 2027
Interim report 2	Data cut 6 years following FPFV 15 Dec 2028
Last patient last visit (LPLV)	15 Dec 2032
End of data collection – defined as data base lock	Q1 2033

Protocol  
 Study ID: NN8640-4515  
 UTN: U1111-1264-8642  
 EU PAS No: Pending

**CONFIDENTIAL**

Date: 15 February 2022  
 Version: 3.0  
 Status: Final  
 Page: 10 of 53

**Novo Nordisk**

Milestone	Planned date
Final report of study results	Q1 2034
Study progress reports	To follow PSUR timelines

### 4.3 Rationale and background

Sogroya® (somapacitan) is a recombinant human GH analog developed by Novo Nordisk, indicated for replacement of endogenous GH in adults with growth hormone deficiency (AGHD).

Replacement therapy with once-weekly somapacitan and once-daily-somatropin differ from endogenous GH release under normal physiological conditions.

In clinical phase 3 trials, IGF-I levels obtained with somapacitan were within the age-adjusted normal reference range with temporary peaks above the upper limit of normal range for a small subset of patients. Importantly, modestly and transiently elevated IGF-I levels in GH replacement therapy have not been linked to adverse effects in published literature nor in the somapacitan phase 3 trials.

Even after over 20 years of adult GH replacement, evidence suggesting that rhGH replacement in adults increases cancer risk or accelerates recurrences of tumours in the hypothalamic-pituitary region remains unclear; With conflicting results in the literature, the overall effect of rhGH replacement on the development of diabetes is also unclear. Somapacitan has been studied in AGHD patients for up to 86 weeks. Thus, the safety information during longer period of treatment is limited.

If patients taking GH replacement report significant QoL benefits and/or there are objective improvements, such as in cardio-vascular risk markers, BMD, body composition, or physical activity tolerance, then GH treatment can be continued indefinitely. Therefore, further investigations, including long-term surveillance studies after regulatory approval are essential to improve our understanding of the safety and effectiveness of prolonged exposure to Sogroya®.

As part of the marketing authorisation of Sogroya®, Novo Nordisk has received a requirement from the Committee for Medicinal Products for Human Use (CHMP) under European Medicines Agency (EMA) to conduct a non-interventional PASS to investigate long-term safety of Sogroya® (somapacitan) in patients with AGHD.

Therefore, as part of the risk management plan for Sogroya® (somapacitan) for treatment of AGHD, the primary aim of this non-interventional study (NIS) is to characterise the long-term safety profile of Sogroya® (somapacitan) with special focus on the important potential risks (diabetes mellitus type 2, neoplasms and medication errors) and additional long-term safety information. Therefore, this PASS may allow a further evaluation of these potential risks in relation to treatment with Sogroya®. Medication errors are of specific interest since some patients will switch from daily GH injections to weekly injections with Sogroya®. Therefore, the PASS may provide information on whether this might lead to medication errors in clinical practice

Only data generated as part of routine clinical practice will be collected in this study.

Protocol  
 Study ID: NN8640-4515  
 UTN: U1111-1264-8642  
 EU PAS No: Pending

**CONFIDENTIAL**

Date: 15 February 2022 **Novo Nordisk**  
 Version: 3.0  
 Status: Final  
 Page: 11 of 53

In order to draw clinically relevant conclusions on long-term safety of Sogroya® (somapacitan), the study will compare data from a non-interventional registry (NordiNet® International Outcome Study (IOS)) study which has been monitoring the long-term use of once daily Norditropin® as a historical comparison group consisting of approximately 2300 AGHD patients.

#### **4.4 Research question and objectives**

##### **4.4.1 Primary objective**

To investigate long-term safety of Sogroya® (somapacitan) therapy in patients with AGHD in the setting of routine clinical practice with special focus on neoplasms and diabetes mellitus type 2.

##### **4.4.2 Secondary objectives**

To investigate safety and clinical parameters of Sogroya® (somapacitan) treatment under routine clinical practice in patients with AGHD.

To investigate safety and clinical parameters of Sogroya® (somapacitan) treatment under routine clinical practice in patients with AGHD for the subgroups childhood-onset GHD and females on oral oestrogen therapy, respectively.

To investigate the number of patients achieving the age-adjusted IGF-I SDS levels up to the upper limit of the normal reference range (0 and +2)

To evaluate the impact of Sogroya® (somapacitan) on patient functioning and wellbeing through a patient reported outcome measure (TRIM-AGHD)

##### **4.4.3 Exploratory objective(s)**

Change in number of different anti-diabetic medication for patients with diabetes mellitus type 2 at baseline.

To evaluate the impact of Sogroya® (somapacitan) on patient sick days and physicians' visits, work and study productivity and the ability to do regular daily activities through a patient reported outcome measure (AGHD WSI).

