### 8.3 Exploratory objective(s)

Change in number of different anti-diabetic medications for patients with diabetes mellitus type 2 at baseline.

To evaluate the impact of Sogroya® (somapacitan) on patient sick days and physician visits, work and study productivity and ability to do regular daily activities through a patient reported outcome measures (AGHD WSI).

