**Figure 1 Study Design**

**Note:** symbol (  ) Represents interim reporting

The study is planned to collect a broad variety of safety and other clinical parameters data generated during routine clinical care visits and other relevant clinical contacts (e.g. phone calls between patient and clinical site) in AGHD patients treated with commercially available Sogroya® (somapacitan). The duration of the study is planned with patient participation for 5 years or longer up to a total study duration of 10 years, if possible. The main purpose of the study is to observe patients for long-term safety. It is however well known that adult patients on GH therapy, often interrupt or discontinue treatment. Due to this expected dropout from treatment, and in the context of the duration of the study, patients switching from or discontinuing treatment with Sogroya® (somapacitan) will be offered continuation in the study in order to collect post treatment data.

The current study will compare data from a non-interventional registry study (NordiNet® IOS) which was monitoring the long-term use of once daily Norditropin® as a historical comparison group consisting of approximately 2300 AGHD patients enrolled in Europe between 2006 and 2016.

The sample size estimation for this study is based on the incidences for neoplasms reported in Nordinet® IOS. It is estimated that a sample size of 400 patients will be required to rule out the doubling of incidence for neoplasms in patients treated with Sogroya® (somapacitan).

Data on concomitant medication, medical history (adult/ childhood onset of GHD), laboratory parameters including but not limited to hepatic, renal, heart and diabetes status as well as data on neoplasms and medication errors will be collected as part of this study if available per routine clinical practice in order to evaluate safety. Other data which are already available in the medical records or being obtained as part of routine clinical practice, such as IGF- I /IGFBP-3 values, measures of body composition and bone health and PROs, will be collected to support the evaluation of clinical parameters.

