### 9.1.1.3 Exploratory endpoints

Endpoint title	Time frame	Unit
AGHD Work Study Impact (WSI)	From baseline (week 0) to end of study*	-10 to +10 Annual rate of sick days and physician visits
Number of anti-diabetic medications for patients with diabetes mellitus type 2 at baseline	From baseline (week 0) to end of study*	count of ATC code

\*End of study will differ from patient to patient, but can be between 1 week and a maximum of 10 years

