#### **Continuous secondary endpoints:**

For the following secondary endpoints, the change will be estimated by length of follow-up and by treatment duration. Patients on oral oestrogen therapy and patients with childhood-onset GHD will be addressed in stratified analyses. The effect of a previous GH replacement therapy on the health-related quality of life will be checked in stratified analyses.

- Change in IGF-I SDS
- Change in weight
- Change in BMI
- Change in waist circumference
- Change in waist-hip ratio
- Change in lipid profile
- Change in HbA1C
- Change in bone density
- Change in bone mineral content
- Change in total body fat mass
- Change in truncal fat mass
- Change in lean body mass
- Change in body fat percentage
- Change in VAT
- Change in liver function
- Change in PRO score (TRIM-AGHD)

Protocol  
 Study ID: NN8640-4515  
 UTN: U1111-1264-8642  
 EU PAS No: Pending

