#### **9.7.2.3 Analysis of exploratory endpoint(s)**

The number of sick days and physician visits in the AGHD WSI will be converted into visits per year. The impact on productivity and ability to do regular activities will be analysed in the same way as the secondary endpoint Change in PRO score (TRIM-AGHD).

The number of anti-diabetic medications will be presented in descriptive tables for the subgroup of patients with diabetes mellitus type 2 at baseline by length of follow-up and by treatment duration.

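### The exploratory objective asks for the change in number of anti-diabetic medications, but the endpoint and its analysis give only the number, over columns that hold different patients

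*Protocol*

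**What the plan says.** The objective is worded as a change in the abstract and in the body: section 4.4.3 reads "Change in number of different anti-diabetic medication for patients with diabetes mellitus type 2 at baseline", and section 8.3 reads "Change in number of different anti-diabetic medications for patients with diabetes mellitus type 2 at baseline".

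The endpoint in section 9.1.1.3 drops that word. It is "Number of anti-diabetic medications for patients with diabetes mellitus type 2 at baseline", with a count of ATC codes as its unit and baseline to end of study as its time frame.

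The analysis in section 9.7.2.3 follows the endpoint: "The number of anti-diabetic medications will be presented in descriptive tables" for the subgroup with type 2 diabetes "at baseline by length of follow-up and by treatment duration".

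Section 9.7.2.2 uses the same two time axes for the continuous secondary endpoints but names the change there: "For the following secondary endpoints, the change will be estimated by length of follow-up and by treatment duration".

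On who will be observed for how long, section 9.1 says "It is however well known that adult patients on GH therapy, often interrupt or discontinue treatment", and adds that patients who switch from or discontinue Sogroya "will be offered continuation in the study in order to collect post treatment data". The footnote to section 9.1.1.3 lets an individual patient's end of study fall anywhere from 1 week to 10 years.

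**The concern.** A change from baseline compares each patient with himself or herself. A table of numbers by time compares groups of patients. The two agree only if the same patients fill every column, or if those who leave have the same average count as those who stay. Here the columns cannot hold the same patients, because follow-up and time on treatment vary widely.

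What is at stake is the reading of one table. Type 2 diabetes is a named focus of the primary objective, and this is the endpoint that tracks how intensively patients who already have it are being treated. A falling row could be read as reassurance and a rising row as a signal, when neither reflects a change in anyone's medication.

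**Working it through.** The protocol gives no figure for this endpoint, so there is nothing to reproduce. The check has three parts.

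**1. The wording side by side**

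| Place | Quantity |
|---|---|
| 4.4.3 and 8.3, objective | change in number |
| 9.1.1.3, endpoint | number |
| 9.7.2.3, analysis | number, by follow-up and by treatment duration |
| 9.7.2.2, continuous secondary endpoints, same axes | change |

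No within-patient change is defined for this endpoint.

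**2. Whether the columns hold different patients**

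Section 6 plans first entry on 15 Dec 2022, last entry on 15 Dec 2027 and the last visit on 15 Dec 2032. Entry therefore spans 5 years and the study 10. Assume uniform entry and no drop-out at all. The share of patients who can be observed t years after entry, for t from 5 to 10, is (10 − t)/5:

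- year 6: 4/5 = 80%
- year 8: 2/5 = 40%
- year 9: 1/5 = 20%

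Later columns are subsets even before anyone leaves. Discontinuation and loss to follow-up (acknowledged in section 9.9) come on top. In the treatment-duration table, only patients treated that long can reach a later column.

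**3. What this does to the tabulated mean**

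Assumed inputs, not in the documents: 100 patients with type 2 diabetes at baseline, 50 on one drug and 50 on three, and no patient's treatment ever changes. The baseline mean is (50×1 + 50×3)/100 = 2.00 and the true within-patient change is 0. With a patients on one drug and b on three still in the column, the tabulated mean is (a + 3b)/(a + b).

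| Loss, one-drug / three-drug | a | b | Tabulated mean | Apparent change |
|---|---|---|---|---|
| 30% / 30% | 35 | 35 | 140/70 = 2.00 | 0 |
| 20% / 40% | 40 | 30 | 130/70 = 1.86 | −0.14 |
| 10% / 50% | 45 | 25 | 120/70 = 1.71 | −0.29 |
| 20% / 60% | 40 | 20 | 100/60 = 1.67 | −0.33 |
| 40% / 20% | 30 | 40 | 150/70 = 2.14 | +0.14 |
| 50% / 10% | 25 | 45 | 160/70 = 2.29 | +0.29 |
| 60% / 20% | 20 | 40 | 140/60 = 2.33 | +0.33 |

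The paired change is 0 in every row. The baseline mean of the patients still in the column equals the tabulated mean, so printing it alongside would expose the artefact at once.

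**The case against.** **The endpoint title may be shorthand.** In the same table the AGHD WSI title also omits the word change, yet its unit runs from −10 to +10 although section 9.2.8.9 gives the scale as 0 to 10, so a change is meant. This is a fair point about drafting style. It does not carry over: the unit here is a plain count, and section 9.7.2.3 sends the WSI productivity and activity items to the TRIM-AGHD change analysis but presents the medications as a number. The time frame does not settle it either, because pure counts such as the number of adverse events carry the same one.

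**Table layout belongs in the statistical analysis plan, which is not shown.** It could add baseline or change columns, and the protocol does not exclude them. But the disagreement between objective, endpoint and analysis lies inside the protocol. The layout also matters little: whether a column holds patients observed at that time or patients grouped by their total follow-up, different columns hold different patients.

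**Patients who stop Sogroya can stay in the study.** This stands in part. It lessens the problem for the length-of-follow-up table. It does not help the treatment-duration table.

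**Other data cover worsening diabetes.** This stands. Change in HbA1c is a secondary endpoint, worsening of a concomitant illness is recorded as an adverse event (9.2.8.5), and section 9.7.2.1 stratifies by history of diabetes. The diabetes primary endpoint is incident disease. No decision hangs on this table.

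A reader might infer that drop-out of heavily treated patients will show up as a reduction in treatment. The documents do not support that. Nothing in them says patients on more anti-diabetic drugs leave more often, and the shift can be zero or go the other way.

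**Conclusion.** The point holds as a mismatch between the objective and the planned endpoint and analysis. Followed as written, differences between the tabulated columns do not measure the change asked for, because they mix any real change with changes in who is being counted.

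The direction and size are not known. Under the assumed half-and-half split, the artefact runs from −0.33 to +0.33 drugs per patient across the loss patterns tried, and is zero when loss is equal. These figures rest on the assumed split, the assumed loss rates and constant treatment, and they illustrate the mechanism rather than forecast it. That later columns contain fewer and different patients does not rest on those assumptions: it follows from the protocol's own dates and follow-up range.

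The importance is low, since the endpoint is exploratory and descriptive and diabetes is also followed by other endpoints.

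**What to change.** In sections 9.1.1.3 and 9.7.2.3, define the endpoint as each patient's change from baseline in the number of distinct anti-diabetic ATC codes, among patients with type 2 diabetes at baseline. At each follow-up length and each treatment duration, tabulate:

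- the change, as fewer / same / more and as a mean
- the number of patients contributing
- the baseline count of those same patients

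State the remaining limit beside the table: pairing removes the effect of differing baseline counts, but not the bias that arises if patients leave because their diabetes worsens. Their intensified treatment would then go uncounted.

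The cost is the wording of one endpoint and one analysis paragraph, and a few extra table rows. No new data are needed: section 9.2.8.7 already requires all concomitant medication at entry and any changes at each visit, preferably with start and stop dates.
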